## PROTOCOL SUMMARY

This research study aims to compare the impact of a financial incentive on improving glycated hemoglobin control in patients with type 2 diabetes mellitus, depending on whether the effort is made individually or with someone's support (family member, friend).

The use of financial incentives to promote behavioral changes that persist over time has been tested in other countries in the region. They have been used to change habits such as smoking, and to lose weight; however, there are no studies that allow to know the impact of this strategy in managing type 2 diabetes mellitus. There are also no clear strategies for determining the amount of financial incentive to be used to promote behavioral changes (adherence to treatment, increasing physical activity, and a healthy diet) in patients with type 2 diabetes mellitus. There are also questions regarding the frequency of the incentives, the type of incentive (cash or other type of reward), the payment method, etc.

This research study is exploratory in nature, as it is oriented to document the implementation process of an intervention focused on reducing weight and glycated hemoglobin in patients with type 2 diabetes mellitus who will receive a financial incentive in three modalities: (1) individual (only the patient receives the incentive), (2) predetermined mixed (the patient and the person who assists him/her in achieving his/her goal receive the incentive and divide it according to what is established by the research protocol), and (3) negotiated mixed (the patient and the person who assists him/her in achieving his/her goal receive the incentive and divide it after negotiating between them the percentage corresponding to each one). The financial incentive will be accompanied with diabetes education.

At the end of the pilot study, qualitative research methods will be used to document the experiences and opinions of research participants on the relevance of the use of financial incentives to promote habits associated with the management of diabetes mellitus.

## 1. INTRODUCTION

Diabetes is a chronic disease presenting an enormous challenge to healthcare systems worldwide. Diabetes management recommendations such as lifestyle changes, increased exercise, and dietary modifications have proven to be an effective way to reduce the long-term consequences and costs of disease. Even though we know that these practices are effective, adherence is poor among patients with diabetes. For example, in Peru, 70% of patients with diabetes have poor glycemic control and only 3.3% meet the optimal control definition according to the recommendations of the American Diabetes Association (ADA), i.e., adequate control of glycemia, LDL cholesterol and blood pressure. [1] In the general population, the values obtained for glycemic control are equally poor. Only 7% of the population has an adequate glycemic control and treatment (measuring fasting blood glucose) and if the criteria are stricter (glycated hemoglobin or HbA1c <7%), then only 0% of the population has adequate disease control. [2] Poor management of a chronic disease such as diabetes is associated with a high risk of chronic complications and comorbidities, raising costs associated with healthcare.

### 1.1. Diabetes prevention

Clinical trials in developed countries and population-based studies have reported preventive care benefits for glycated hemoglobin control in patients with diabetes. [3] Preventive strategies focused on diabetes management can add up to four years of life expectancy to a 50-year-old person, reduce diabetes-related morbidity, and significantly increase well-being.[4] Despite the medical consensus on the efficacy of preventive measures, patient medication adherence worldwide is quite poor. A research study carried out in seven Latin American cities on subjects with type 2 diabetes showed that 78% of the individuals were aware of their condition, 33% were receiving treatment, and only 5% met therapeutic goals.[5] A research study carried out in Lima showed similar results: 71% were aware of their disease, 40% were receiving treatment and only 7% met therapeutic goals.[2]

Low levels of adherence can be caused by behavioral factors of patients with diabetes, preventing them from doing what is best for their health. Factors such as failure to control or poor planning capacity for the future could contribute to this low level of prevention; in addition to traditional factors such as access to healthcare services and lack of economic resources to pay for prevention. In this context, the use of pure and mixed financial incentives could help with the problems patients face in doing what is in their best interest to take care of their health.

## **1.2. Incentives in Healthcare**

Factors preventing the person with diabetes from seeing the benefits of taking care of him/herself could change if a reward is offered to the person with diabetes that gives him/her a present benefit and helps him/her deal with everyday efforts to take care of him/herself. The literature on incentives suggests that the effect of incentives to modify behavior depends on several interconnected factors.[6] The payment of monetary incentives based on compliance with certain prevention measures reduces the cost of disease management; however, it may end up displacing the internal individual motivation that is key to the self-care of a patient with a chronic disease. Both the design and mode of delivery of incentives can affect the success of the intervention.

The existing literature does not allow us to state if monetary incentives promote lasting behavioral change and there are many doubts about their relevance for chronic disease management.[7] Monetary rewards can help with short-term habit formation as the benefits of prevention accrue over longer periods of time. Prevention today can lead to reduced prevention efforts tomorrow, and monetary incentives can help to consolidate this initial process.[8] However, cash rewards may not be high enough to drive initial changes, especially once the initial effort effects dissipate. It can also be argued that monetary incentives can be effective in rewarding concrete results, but less effective in rewarding processes such as checking blood sugar levels every day or exercising.

Behavioral science literature states that incentives given to individuals should be: frequent and in small amounts, be positive rather than negative, and promote the connection between short- and long-term goals.[9-11] Evidence on the impact of financial incentives is growing as there are several interventions that seek to demonstrate the benefits of using financial incentives for

adherence to substance abuse treatment,[12] and to promote weight loss and smoking cessation.[13,14] More recently, studies regarding the effects of incentives on blood donation, organ donation, HIV treatment, and other pro-social behaviors have been carried out.[15,16-17]

On the other hand, there are behaviors in which it is not easy to measure the effort made by the patient to reach them. Financial incentives may not be effective as in the case of weight loss, since two people may lose the same amount of weight in the same amount of time, but the effort to reach the goal probably differed. Some reviews indicate that financial incentives are effective in the very short term for preventive care and in well-defined behavioral interventions; furthermore, there is enough evidence to affirm that financial incentives are effective for the long-term lifestyle change required for health promotion. [18]

Little is known about the effect of incentives at an individual level when such incentives are given to peers, a family member or friend who provides support in this process. These incentives are called "mixed incentives" and can also positively influence individual behavior, as they use the feeling of connection with others and responsibility to support each other.

### **1.3. Diabetes and Financial Incentives**

There have been very few research studies evaluating the effectiveness of financial incentives in patients with diabetes and the impacts of this disease. A randomized clinical trial with a small sample size conducted in the United States used financial incentives in African American veterans with poor glycemic control and found that the incentive slightly improved HbA1c results by 1 to 2% over 6 months; however, the result was not statistically significant.[20] Other research studies have demonstrated the role of financial incentives in stimulating and maintaining weight loss in people who wanted to lose weight. While one research study found that lottery-style incentives could facilitate weight loss compared to a control group, the effect was not maintained after the incentive was removed.[21] However, in another research study in which incentives were linked to group success, group-incentive participants not only lost more weight, but also maintained weight loss better than the control group.[21] These results are interesting, and suggest further research study is needed on incentives in diabetes management.

#### **1.4. Do financial incentives work in Latin America?**

Conditional cash transfers (CCTs) have become a widely used method by governments as a strategy to try to reduce poverty, improve education, and other major aspects of development (such as child nutrition), particularly in Latin American countries.[8] Several Latin American countries have some CCT programs, such as Mexico, Honduras, Nicaragua, Brazil, Colombia and Peru. Recent evaluations of the impact of these programs show that health indicators are improving as an outcome of them. [22] It is important to clarify that most of the outcomes come from process indicators and are directly related to the use of healthcare services.

The first CCT program implemented in Latin America was "Oportunidades" in Mexico, requiring children and pregnant women to take nutritional supplements and attend certain healthcare services. An evaluation of the program found an association between a greater number of transfers received and significantly better outcomes in many areas, including short- and long-term memory, visual integration, and language development.[23]

"Atención a Crisis", a CCT in Nicaragua, is conditional on the fact that families receiving the money must ensure that preschoolers attend their medical appointments on a regular basis and get vaccination and micronutrients/food supplements when necessary. The evaluation of this program found significant improvements in healthcare outcomes. Interestingly, these improvements continued even two years after the program and cash transfers ceased.[24] "Juntos", the CCT in Peru was designed as a poverty reduction initiative through increasing the demand for public services in exchange for fulfilling certain responsibilities related to health and education, and pregnant women and mothers of children aged below 5 are required to use certain healthcare services. Families benefiting from "Juntos" receive a cash transfer of 200 Nuevos Soles every two months. "Juntos" is a relatively new program and there are not many published research studies describing its impact. A World Bank report found that overall household consumption increased by 33% and poverty levels were reduced by 14%. [24] In addition, it found that "Juntos" increased the likelihood that children in beneficiary households would comply with their growth and development check-ups (CRED, by its Spanish acronym), seek professional help in case of any illness, and the likelihood that pregnant women would give birth in a health facility attended by an expert professional.

To better understand the impact of cash component of CCT, it is important to recognize that these programs take advantage of strong family structures in Latin America, and leverage the responsibility of their members for health improvement. The person in charge of ensuring that the

requirements are met is not only encouraged to be responsible because of an individual reward, but to improve the family's situation. This underscores the potential of using social capital and accountability to design more effective policies, and will be an important element of our approach. As has been demonstrated in CCT programs, the use of financial incentives has the potential to reach long-term effects that last beyond the duration of the incentive program, leading to greater public health impact.

Recent research analyzes factors explaining disease self-management in people with diabetes and hypertension using cross-sectional databases for five Latin American countries.[25] The findings suggest that income level is the most important component in reducing differences in the impact of preventive practices. In the five countries of the study, the role of income in the diabetes self-management of diabetic patients ranged from 23% in Chile to 58% in Argentina. It is interesting to note that access to healthcare services (insurance availability) [26] and knowledge about diabetes self-management have a significantly lower impact than income. All these outcomes suggest that cash payment may play an important role in changing an individual's behavior in the case of patients with diabetes.

## **1.5. Justification**

Clinical trials in developed countries and population-based studies indicate that there are many benefits of preventive care in patients with diabetes.[3, 27] Despite the medical consensus on the effectiveness of preventive measures, worldwide it is difficult to reach control targets in patients with diabetes. The available data clearly emphasize the need for a research study on what methods are needed for diabetes prevention today, and why it is needed specifically in Latin America and other resource-poor settings.

Globally, very few studies have been conducted to evaluate the effectiveness of incentives in diabetes. In this application, we aim to explore the role of incentives in changing the behavior of people with type 2 diabetes. Cost savings or cost-effective interventions can avoid the economic impact of long-term complications of diabetes, such as retinopathy, nephropathy, neuropathy and cardiovascular diseases, as well as short-term complications, such as hospitalizations due to poor glycemic control.[28]

In our research study we will apply financial incentives to promote behavioral change in our patients in order to improve their glycemic control.

## 2. RESEARCH OBJECTIVES

The outcomes of this research study will be used to design a randomized clinical trial aimed at evaluating the impact of the use of monetary incentives in patients with type 2 diabetes mellitus. For this purpose, we first have to answer two research questions, as specified below.

### **General Objective:**

To compare the implementation processes of three interventions that use financial incentives to promote behavioral changes in patients with type 2 diabetes mellitus in order to identify barriers and facilitators linked to the implementation process of each intervention.

### **Specific Objectives**

- To document patient experience in the study of financial incentives.
- To document the experience of people accompanying patients with type 2 diabetes mellitus.
- To test the acceptability and clarity of instructional material used to promote behavioral change.
- To test the feasibility of reaching the proposed clinical goals (weight loss and glycated hemoglobin).
- To test the "sufficiency" of the incentive amount given to both the patient and the patient's companion, in order to promote behavioral changes.
- To explore the sustainability of the companion's participation for 9 months.
- To explore activities that could make the companion more effective in helping the patient manage his/her diabetes.
- To explore whether the patient is able to keep a daily record of the effort made in managing his/her diabetes.
- To evaluate the feasibility of packaging and implementing a future clinical trial, which will evaluate the impact of the use of monetary incentives in patients with type 2 diabetes mellitus.

### **3. RESEARCH METHODOLOGY**

#### **3.1. Research design**

Pilot study testing the feasibility of implementing three types of intervention with financial incentives in a randomized fashion.

#### **3.2. Research site**

Endocrinology Outpatient Services of the Hospital Nacional Arzobispo Loayza.

#### **3.3. Study population, selection criteria**

The study population in general will be patients with type 2 diabetes mellitus who meet the inclusion criteria and people in their social environment who consent to participate in the role of companions throughout the intervention.

##### **3.3.1 Inclusion criteria for the patient**

Subjects will be eligible if

1. They have a diagnosis of type 2 diabetes mellitus,
2. They aged 18 to 70 years,
3. They receive treatment with Metformin or their treatment consists of dietary changes.
4. They have a body mass index between 25kg/m^2 to 39.9 kg/m^2 (range that includes from overweight to severe obesity),
5. They are able to consent,
6. They are not fulfilling the role of a companion in the framework of this pilot study.
7. They do not have blindness, amputations or foot ulcers nor are receiving dialysis as a consequence of diabetes mismanagement.

##### **3.3.2 Inclusion criteria for the companion**

The companions will be chosen by the patients and must also:

1. Aged 18 to 70 years,
2. Not have any physical or mental condition that would prevent them from fulfilling the role in assisting the participant to lose weight,
3. Have availability of time and commitment to support the participant in achieving his/her weight loss goals.
4. Be able to consent.

Consent to participate in the research study will be signed after confirming all inclusion criteria have been met.

### **3.3.3 Exclusion criteria**

- Subjects will be excluded from enrollment if they have cancer or another severe comorbidity.
- Subjects will be excluded if they report pharmacological treatment for weight loss or corticosteroids.
- Subjects will be excluded if they are pregnant.

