#### *Intervention 1: Individual Incentives.*

1. Participants will receive information about the study, specifying that they will receive a reward of 150 soles (about 25% of the minimum wage) at each meeting if they have managed to lose one kilogram in a two-week period. The meetings will take place every two weeks for three months.
2. An initial assessment will be made to determine their weight and the results of their HbA1c will be provided.
3. A plan will be made to determine how many kilograms they should have at each biweekly meeting (Annex 3).
4. Education on nutrition and physical activity will be provided.

5. A manual with information on nutrition and physical activity for people with diabetes interested in losing weight will be given, including tips for loosing weight and a weight loss plan for a two-week period (Annex 4). The DE will manage an "ideal" weight loss plan for the patient throughout the 3 months of the study.
6. They will be given a diary to enter their daily diet and physical activity. The information in this diary will be the starting point to discuss with the diabetes educator at each session about the barriers and achievements in the implementation of the weight loss plan (Annex 4).
7. In addition to the introductory meeting, they will attend seven follow-up sessions (See Figure 1) and a final one in which he/she will be rewarded with the same amount (150 soles) if he/she managed to lower their HbA1c by at least 1%.

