**Figure 1: Patient route map**

*Intervention 2. Mixed incentives: Set up by researchers*

1. Participants and their companions will receive information about the study, specifying that they will receive a reward of 150 soles (about 25% of the minimum wage) at each meeting if they have managed to lose one kilogram in a two-week period. The meetings will take place every two weeks for three months. The reward will be divided 50% for the participant and 50% for the companion.
2. An initial assessment will be made to determine the patient's weight and the results of his/her HbA1c will be provided.
3. A plan will be made to determine how many kilograms they should have at each biweekly meeting (Annex 3).
4. Education on nutrition and physical activity will be provided orally and/or with the support of audiovisual material.
5. A tri-fold leaflet will be given to the companion to guide his/her support (Annex 5).
6. A manual with information on nutrition and physical activity for people with diabetes interested in losing weight will be given to the patient, as well as tips and the weight loss plan per fortnight. The diabetes educator will manage an "ideal" weight loss plan for the patient throughout the 3 months of the study (Annex 4).
7. They will be given a diary to enter their diet, which will be the starting point to discuss with the diabetes educator at each session about the barriers and achievements in the implementation of the weight loss plan (Annex 4).
8. In addition to the introductory meeting, they will attend seven follow-up sessions and a final one in which he/she will be rewarded with the same amount (150 soles) if he/she managed to lower their HbA1c by at least 1%.

*Intervention 3. Mixed incentives: Set up by participants*

1. Participants and their companions will receive information about the study, specifying that they will receive a reward of 150 soles (about 25% of the minimum wage) at each meeting if they have managed to lose one kilogram in a two-week period and if the companion supports the process by attending all the biweekly follow-up meetings. The meetings will take place every two weeks for three months. The participant and the companion must negotiate on the day of the meeting in which the reward is given how they will distribute the amount received, specifying that the maximum that one party can receive is 80% and the minimum 20% of the total amount.

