### **Arm1: Individual Incentives**

Participants will be required to come every 2 weeks to measure their weight and to collect a blood sample for glucose measurement with a glucometer. Weight will be measured in fasting conditions, using the same scale and at the same time as the previous visit.

Each participant will attend a total of 8 sessions (including the initial meeting). In sessions 2 to 7 the diabetes educator will weigh them to see if they reached the goal.

- ***If they reached the goal:*** They will be rewarded and asked about the actions taken to reach their goal. In addition, suggestions for improving their nutrition and diabetes management will be reviewed. For this purpose, the information entered by the participants in their diary will be used. They will also be asked about their physical activity, adherence to treatment and changes in their eating habits. If they have received a reward in the previous session, they will be asked about how they used that reward.

- **If they did not reach the goal:** They will be asked about the actions they took to lose weight and the main challenges in implementing them. For this purpose, the information entered by the participants in their diary will be used. Suggestions for improving their nutrition and diabetes management will be reviewed. They will also be asked about their physical activity, adherence to treatment and changes in their eating habits.
- The patient will fill out a diabetes self-management questionnaire at each session (See Annex 4).

In session 7, a blood sample will be collected to measure his/her Hba1c. The results will be given in session 8 (last session) in which he/she will be rewarded if his/her Hba1c has dropped at least 1% since the beginning of the study (See Annex 7).

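### In the protocol body, the fortnightly weight-loss reward has no clinical stopping condition, and follow-up sessions list no question about pregnancy or new severe illness

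*Combined protocol and SAP*

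**What the plan says.** Section 3.3.3 excludes pregnancy ("Subjects will be excluded if they are pregnant") and serious illness ("Subjects will be excluded from enrollment if they have cancer or another severe comorbidity").

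Section 3.5 offers a "reward of 150 soles (about 25% of the minimum wage) at each meeting if they have managed to lose one kilogram" over two weeks. In arm 2, "The reward will be divided 50% for the participant and 50% for the companion". Arm 3 adds a condition, "if the companion supports the process by attending all the biweekly follow-up meetings", and lets the pair negotiate shares between 20% and 80%.

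Section 3.6.2 sets out the visits. For arm 1, "In sessions 2 to 7 the diabetes educator will weigh them to see if they reached the goal", and "They will also be asked about their physical activity, adherence to treatment and changes in their eating habits". Arm 1 patients also complete a self-management questionnaire at each session, for which Annex 4 is cited. Arms 2 and 3 have a short self-report questionnaire on adherence and, in most branches, activity and diet. All arms have a glucometer reading, and HbA1c is measured at session 7.

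Three other provisions touch on safety:

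- Section 5.10 has staff trained to notice and report adverse events, which the Principal Investigator collects.
- Section 5.9 lets a protocol change go ahead before ethics review when participants need protecting.
- Section 3.7 advises patients, where needed, to see their own physician about what their results mean.

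**The concern.** The concern is patient safety. The trial pays people to lose weight, at about a quarter of the minimum wage per target. The plan does not enrol people for whom that could be unsuitable because of pregnancy or severe illness, but the same conditions can begin during three months of follow-up. Patients may be 18 to 70, and the eligibility text states no sex restriction and no contraception requirement.

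If staff follow the stated rule exactly, a patient in that position remains on the weight-loss target and is paid for meeting it. Weight lost through illness would also be paid as success. Staff are free to act on what they notice, but nothing in the body tells them to ask or to suspend the target. In arms 2 and 3 the companion also has money at stake and has signed a commitment to support the plan, so waiting for the patient to volunteer the information is a weak safeguard.

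**Working it through.** The plan gives no figure to reproduce here. The check is a reading of the text, followed by simple arithmetic on what stays on offer.

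**Step 1: is either condition asked about after entry?** Sections 3.6.2 (arms 1 to 3) list weight, glucose, diary review, actions taken, difficulties met, physical activity, adherence, eating habits and use of earlier rewards. None of these is a question about pregnancy or a new severe illness.

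**Step 2: does any clinical condition stop the reward?** The fortnightly reward depends on the 1 kg loss and, in arms 2 and 3, on the companion's presence or attendance. The body gives no withdrawal criterion, weight floor, glucose threshold or other clinical stop. Section 4.10 says only that no major problems are expected.

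**Step 3: do the nearest safeguards fill the gap?** Section 5.10 could bring a severe illness to light, but it attaches no action to the target, and staff may not regard a pregnancy as an adverse event. Section 5.9 concerns changes to the protocol, not conduct at a visit. Section 3.7 concerns the interpretation of results. None of them pauses the target.

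**Step 4: what stays on offer?** Inputs: 150 soles and 1 kg per target, two-week spacing (section 3.5); weigh-ins at sessions 2 to 7 (section 3.6.2).

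Number of weigh-ins = 7 − 2 + 1 = 6. For a condition starting after session k (k = 1 to 6), targets left = 7 − k, and soles left = 150 × (7 − k).

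| Onset after session | Targets (kg) left | Weeks | Soles left | Minimum wages |
|---|---|---|---|---|
| 1 | 6 | 12 | 900 | 6 × 0.25 = 1.50 |
| 2 | 5 | 10 | 750 | 5 × 0.25 = 1.25 |
| 6 | 1 | 2 | 150 | 1 × 0.25 = 0.25 |

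Section 3.5 instead describes an introductory meeting, seven follow-up sessions and a final one. If all seven carry a weight target, the maximum is 7 × 1 = 7 kg and 7 × 150 = 1,050 soles. Both totals leave out the separate 150 soles for HbA1c.

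These amounts are per patient in arm 1 and per pair in arms 2 and 3. The patient's own share, from one target left to the maximum, is:

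- Arm 1 (100%): 150 to 900 soles, or up to 1,050 with seven targets.
- Arm 2 (50%): 75 to 450 soles, or up to 0.5 × 1,050 = 525.
- Arm 3 (20% to 80%): 0.2 × 150 = 30 to 0.8 × 900 = 720 soles, or up to 0.8 × 1,050 = 840.

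**The case against.** The strongest reply is that the detail may sit in documents not seen here. The per-session questionnaires and the weight plan are in annexes, and consent pages are a usual place for withdrawal conditions. That stands, and it limits the point to the protocol body. If a session form already asks, the asking half is settled by citing it. A pause rule would still need to be stated or pointed to.

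Second, section 3.3.3 belongs to the selection criteria, so nothing in it is wrong. A reader might infer that the exclusions continue through follow-up and that the plan breaches its own rule. The text does not settle this: the severe-illness item is tied to enrolment and the pregnancy item is silent on timing. The point needs neither reading.

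Third, there is real oversight. A diabetes educator sees each patient every two weeks and manages an individual weight-loss plan, and a new severe illness would fall under adverse-event reporting. That makes it likely that many cases would be noticed. It does not tell anyone what to do about the target.

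Fourth, a rule under which a positive answer stops payment gives patients a reason to conceal. This is a genuine cost, so whether to adopt the rule is a judgement.

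A reader might also extend the point to the remaining exclusion: "Subjects will be excluded if they report pharmacological treatment for weight loss or corticosteroids". No comparable harm from continuing the target is shown for a newly started drug, and the existing questions about adherence and actions taken could bring one to light. That extension is not made here.

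**Conclusion.** The gap is real but modest, and worth considering. In the protocol body, the weight-loss reward has no clinical stop, and two conditions that bar entry are not asked about afterwards. For an affected patient or pair, what stays on offer runs from one target (1 kg, 150 soles) to six (6 kg, 900 soles), or seven (7 kg, 1,050 soles) if section 3.5 governs the count. These figures describe the payment schedule, not the amount of harm.

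The documents give no event rate. The assumption is few cases, possibly none, among 45 patients over three months.

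Two stronger conclusions might be drawn and are not supported. One is that the weight or HbA1c comparison would be distorted: nothing in the documents allows a shift to be estimated, and none is claimed. The other is that information not collected at a visit is lost for good: a pregnancy or diagnosis can usually be asked about later. The reason to ask at the visit is to act in time.

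Confidence is medium, because the annexes and consent pages were not available.

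**What to change.** In section 3.6.2, for all three arms, add at each weigh-in a question on pregnancy (where applicable) and on new severe illness, or cite the session form if it already asks. Then add one rule: if either is present, pause the weight-loss target and its reward, let the patient (and companion) keep rewards already earned, inform the Principal Investigator, and refer the patient to the attending physician. In section 5.8.1, report the number of paused patients by arm beside the weight results. No change to the analysis set is needed.

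The cost is about a minute per visit, one sentence in the procedures and one row in a table. The main downside is some under-reporting, because answers are self-reported and a positive one stops payment. Keeping earned rewards softens this but does not remove it.
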